The protocol is also being amended to add updated RANO criteria specifically for low grade glioma (RANO-LGG; Wen 2017) as the basis for independent review. These more recent RANO-LGG criteria allow for the identification of measurable target lesions in patients with LGG that may not be gadolinium enhancing and are best seen by T2/FLAIR imaging sequences. These updated RANO - LGG criteria will be utilized in supplemental independent RANO response determination for those patients with LGG. Note that the independent response determinations that were originally intended to be applied using the older RANO criteria will be retained for analysis purposes. Also note that the response category of 'minor response' will not be used in this trial.

Changes in the protocol:

Changes to specific sections of the protocol are shown in the track changes version of the protocol using strikethrough red font for deletions and red underline for insertions:

- List of Abbreviations Table: updated to include PIP and RANO.
- Removal of named contact details and integrated signature pages in alignment with current Novartis template and standards.
- Section 3.1.2: Amended to match the clinical measures in the current approved PIP.

- Appendix 15.2: Added updated RANO criteria for LGG patients (RANO-LGG) and removed the minor response category in the “Response assessment of target lesions” table as it is not used in this clinical trial.

IRBs/IECs

A copy of this amended protocol will be sent to the Institutional Review Board (IRBs)/Independent Ethics Committee (IECs) and Health Authorities.

The changes described in this amended protocol require IRB/IEC approval prior to implementation.

Amendment 10 (04-Apr-2019)

Amendment Rationale

As of 06-Feb-2019, 85 patients have received study treatment in 8 countries; Part 1 dose escalation has enrolled 27 patients and is closed to enrollment. Based on the data from these 27 subjects, no maximum tolerated dose was established in this pediatric population and the recommended Phase 2 doses (RP2Ds) for dabrafenib monotherapy were determined based on exposure target as 5.25 mg/kg/day for patients < 12 years old and 4.5 mg/kg/day for patients ≥ 12 years old, divided into two equal daily doses, and not to exceed adult dose.

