Subjects with nonmeasurable enhancing disease whose lesions have significantly increased in size and become measurable (minimal bidirectional diameter of ≥ 10 mm and visible on at least two axial slices that are preferably, at most, 5 mm apart with 0-mm skip) will also be considered to have experienced progression. The transition from a nonmeasurable lesion to a measurable lesion resulting in progression can theoretically occur with relatively small increases in tumor size (e.g., a 9 X 9mm lesion [nonmeasurable] increasing to a 10 X 11mm lesion [measurable]). Ideally, the change should be significant (>5 mm increase in maximal diameter or $\geq 25\%$ increase in sum of the products of perpendicular diameters of enhancing lesions).

In general, if there is doubt about whether the lesion has progressed, continued treatment and close follow-up evaluation will help clarify whether there is true progression. If there is uncertainty regarding whether there is progression, the patient may continue on treatment and remain under close observation (e.g., evaluated at 4-week intervals). If subsequent evaluations suggest that the patient is in fact experiencing progression, then the date of progression should be the time point at which this issue was first raised.

Response assessment in neuro-oncology (RANO) criteria for low-grade gliomas (LGG) (RANO-LGG).

During the course of the trial, revised RANO criteria specific for LGG have become available (RANO-LGG; [Wen, 2017](#)). These criteria will also be used for central independent review per Protocol Amendment v11. This review is in addition to the previously performed review using RANO ([Wen, 2010](#)).

According to the updated RANO-LGG criteria, the definition of measurable disease is modified. Measurable disease is defined as bidimensionally visible lesions on T2 weighted fluid-attenuated inversion recovery (FLAIR) scans with clearly defined margins, with two perpendicular diameters of at least 10 mm (or at least two slice thicknesses with no gaps

between slices), visible on two or more axial slices that are preferably, at most, 5 mm apart with 0mm skip.

Non-measurable disease includes all other lesions, including:

- unidimensionally measurable lesions
- lesions with maximal perpendicular diameter that is both < 10mm and less than two slice thicknesses with no gaps between slices
- lesions with borders that cannot be reproducibly measured
- dural, bony skull metastases

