Progressive disease (PD)	Significant and unequivocal increase of the non-measurable lesions on T2/FLAIR or increase of enhancement on T1 images
Not Evaluable (NE)	Not evaluable will be used in exceptional cases where one or more non-measurable lesions cannot be assessed or have been assessed using a different method than baseline, in absence of progressive disease documentation

A lesion not present at baseline and appearing at any follow-up evaluation timepoint (TP) is considered a New Lesion.

The Investigator/local reader will characterize each new lesion as either equivocal or unequivocal (progressive disease). If unsure of a new lesion, the Investigator/local reader will mark it as equivocal and assess at the next timepoint if the lesion is present. Appearance of an equivocal new lesion does not lead to a determination of PD. If repeat scans confirm the lesion is unequivocal, progression should be retrospectively assigned back to the first observation of the lesion.

The evaluation of overall lesion response at each assessment is a composite of the target lesion response, non-target lesion response, the presence of new lesions, corticosteroid use relative to baseline, and clinical status as assessed by investigator and supported by the ECOG/Karnofsky Performance Scale as shown below

Overall lesion response at each assessment (measurable and non-measurable disease at baseline)

Criterion	Complete Response	Partial Response	Stable Disease	Progressive Disease
T2/FLAIR (target lesions)	None	≥50% decrease in SPPD compared to baseline	<50% decrease Compared to baseline but <25% increase in SPPD compared to Nadir	≥25% increase in SPPD compared to Nadir**
T2/FLAIR (non-target lesions)	None	Stable or improved	Stable or improved	Unequivocal PD**

Criterion	Complete Response	Partial Response	Stable Disease	Progressive Disease
T1 gadolinium enhancing disease	Stable or improved	Stable or improved	Stable or improved	Unequivocal increase**
New Lesions	None	None	None	Present*
Corticosteroids compared to baseline	None	Stable or decreased	Stable or decreased	NA***
Clinical Status compared to baseline	Stable or improved	Stable or improved	Stable or improved	Worsened**
Requirement for Response	All	All	All	Any**

Complete Response (CR):

All of the following criteria must be met:

- a. Complete disappearance of the lesion of T2 or FLAIR imaging. . In the absence of a confirming scan at least 4 weeks later, this scan will be considered only stable disease.

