- b. No new lesions, no new T2 or FLAIR abnormalities apart from those consistent with radiation effects, and no new or increased size of enhancement
- c. Participants must be on no steroids or on physiologic replacement doses only.
- d. Stable or improved clinically, for clinical signs and symptoms present at baseline and recorded to be disease related

Partial Response (PR):

All of the following criteria must be met:

- a. Greater than or equal to 50% in the product of perpendicular diameters of the lesion on T2 or FLAIR imaging sustained for at least 4 weeks compared with baseline.
- b. No new lesions, no new T2 or FLAIR abnormalities apart from those consistent with radiation effects, and no new or increased size of enhancement
- c. Patients should be on a corticosteroid dose that should not be greater than the dose at time of baseline scan, and should be stable or improved clinically.

Stable Disease (SD):

All of the following criteria must be met:

- a. Does not qualify for CR, PR, MR or progression.
- b. Stable area of non-enhancing abnormalities on T2 or FLAIR imaging
- c. No new lesions, no new T2 or FLAIR abnormalities apart from those consistent with radiation effects, and no new or increased size of enhancement
- d. Patients should be on a corticosteroid dose that should not be greater than the dose at time of baseline scan, and should be stable or improved clinically.

Progressive Disease (PD):

- a. A 25% increase of the T2 or FLAIR non-enhancing lesion on stable or increasing doses of corticosteroids compared with nadir, not attributable to radiation effect or to comorbid events
- b. Significant and unequivocal increase of the non-measurable lesions on T2/FLAIR
- c. Development of new lesions or increased size of enhancement
- d. Definite clinical deterioration not attributable to other causes apart from the tumor, or decrease in corticosteroid dose
- e. Failure to return for evaluation because of death or deteriorating condition, unless caused by documented non-related disorders.

If there is uncertainty regarding whether there is progression, the patient may continue on treatment and remain under close observation (e.g., evaluated at 4-week intervals). If subsequent evaluations suggest that the patient is in fact experiencing progression, then the date of progression should be the time point at which this issue was first raised.

Response Status Unknown: Not Evaluable (NE):

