2.6 Analysis of the key secondary objective

2.6.1 Secondary endpoint

The All Treated population will be used for all efficacy analyses.

Overall response rates along with 95% confidence intervals will be separately calculated for all the disease cohorts including the LGG, HGG, LCH and Other disease cohorts.

Efficacy assessments are based on RANO criteria for LGG and HGG patients. In addition, for LGG patients, the updated RANO criteria will be used for independent review. For LCH patients, the response assessment criteria are described in Appendix 2 of the protocol. For patients with other solid tumor, efficacy assessments are based on RECIST 1.1.

Refer to study GSK SAP for additional details.

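### RANO-LGG serves only the supplemental independent review, yet its text gives the new-lesion call to the open-label site

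*Protocol*

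**What the plan says.** Three places say where RANO-LGG is used, and they agree.

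- Protocol, Amendment 11 rationale: "These updated RANO - LGG criteria will be utilized in supplemental independent RANO response determination for those patients with LGG".
- Protocol, Appendix 2 (Section 15.2), RANO-LGG: "These criteria will also be used for central independent review per Protocol Amendment v11". The note under the 2010 RANO heading says the same, and both places describe this read as additional to the independent review already done under the 2010 criteria.
- SAP Section 2.6.1, after naming RANO as the basis for LGG and HGG: "In addition, for LGG patients, the updated RANO criteria will be used for independent review".

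The RANO-LGG text then says who judges a new lesion: "The Investigator/local reader will characterize each new lesion as either equivocal or unequivocal (progressive disease". If the judgement is uncertain, "the Investigator/local reader will mark it as equivocal and assess at the next timepoint if the lesion is present". An equivocal lesion is not progression. If repeat scans show that it is unequivocal, progression is dated back to when it was first seen.

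The call feeds the composite. The overall-response table requires no new lesions for CR, PR and SD, and the written definitions of those categories repeat it: "No new lesions, no new T2 or FLAIR abnormalities apart from those consistent with radiation effects". One other component is openly a site input: "clinical status as assessed by investigator and supported by the ECOG/Karnofsky Performance Scale".

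**The concern.** An independent read in a single-arm, open-label trial is useful because the images are judged by someone outside the treating site. Clinical status and steroid dose have to come from the site. Deciding whether a spot on a scan is a new tumour lesion does not; that is image reading.

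The category also does not match what sites were asked to use. In the 2010 RANO text, any new lesion is progression. That text has a general provision for uncertain progression but no equivocal class for new lesions. RANO-LGG was added in August 2020, with Part 2 already closed to enrolment. Followed to the letter, the rule would need a local label that the 2010 criteria did not call for, or one assigned retrospectively by an unblinded site.

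At stake is how far the RANO-LGG response rate can be presented as independent of the investigator result. If both reads share the new-lesion call, part of their agreement is built in.

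**Working it through.** The plan states no figure on this point, so the check is mainly a comparison of text.

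**Step 1. Who applies RANO-LGG?** Every passage that assigns a use assigns it to the independent review. None asks investigators to re-read scans under it, and the Time and Events tables contain no such task. That it is used nowhere else is inferred from this consistent wording. The general references to Appendix 2 for investigator assessment (Protocol Sections 2 and 5.3.3.3) are not specific enough to overturn it.

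**Step 2. Who makes the new-lesion call?** The investigator or local reader, named twice. No passage gives the central reader a call of its own or a rule for disagreement.

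**Step 3. When does the label change the response rate?** Assume that an equivocal lesion does not by itself block a response, and that responses count only up to progression (Appendix 2, best overall response, stated in the RECIST part).

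| New lesion | Label | Result |
|---|---|---|
| At or before confirmation | Unequivocal | PD; no confirmed response |
| At or before confirmation | Equivocal, later confirmed | PD dated back to first sighting; a response seen afterwards is lost |
| At or before confirmation | Equivocal, never confirmed | Not PD; response stands if all other conditions are met |
| After confirmation | Either | Response stands; only the progression date can change |

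The local label therefore changes responder status only in the first three rows, where site and centre would classify the lesion differently and the outcomes diverge. An equivocal label cannot create a response: the shrinkage, enhancement, non-target, steroid and clinical conditions must also be met.

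**Step 4. Size.** Inputs from the Amendment 11 rationale: 17 LGG subjects in Part 2; 27 subjects in Part 1, two of them with miscellaneous tumours. The interval is exact (Protocol Section 5.3.3.3), from beta quantiles: lower = Beta(0.025; x, n−x+1), upper = Beta(0.975; x+1, n−x). As a check, this reproduces Table 5-2: 4/10 gives 12.2–73.8% and 14/35 gives 23.9–57.9%.

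- One subject in Part 2: 1/17 = 5.9 percentage points.
- Illustration with assumed response counts, which are not in the documents: 5/17 = 29.4% (10.3–56.0) against 6/17 = 35.3% (14.2–61.7); 7/17 = 41.2% (18.4–67.1) against 8/17 = 47.1% (23.0–72.2).
- Pooled cohort (SAP Section 2.1): the Part 1 LGG count is not given. It cannot exceed 27 − 2 = 25, so the pooled denominator is at most 17 + 25 = 42, and one subject is between 1/42 = 2.4 and 5.9 points.

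**The case against.** A reader might infer that the independent LGG response rate depends on the investigator's judgement, so that the read is not independent. The documents do not go that far. The text names who characterises a new lesion; it does not say that the label is sent to the central reader or binds that reader. The CR, PR, SD and PD definitions name no local reader for lesions and can be applied centrally as they stand. Protocol Section 5.3.3.3 promises assessment by an independent reviewer, and imaging detail is deferred to the SPM and an imaging manual. Wording carried over from a template is at least as likely as a planned dependence. These points stand, and they are why the concern is one of wording that permits the dependence.

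A reader might also infer that a local equivocal label protects a later partial response. It does so only if the lesion is never confirmed; otherwise back-dating places progression before that response. Back-dating applies only to lesions first called equivocal.

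The impact is limited too. The anti-tumour endpoint is investigator-assessed (Protocol Section 2), independent review is supportive, the earlier independent determinations under 2010 RANO are retained, and no hypothesis is tested. Investigator-assessed clinical status remains in the composite whatever is done about lesions, so complete separation from the site is not available.

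What remains is that, in criteria reserved for central review, the only person named for an image judgement is the local reader, twice, and nothing in the documents corrects this.

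**Conclusion.** The inconsistency is real and narrow. Read literally, Appendix 2 takes one imaging component of the supplemental independent LGG response from the open-label site, under a class absent from the 2010 RANO text that investigators use. Whether this happens in practice cannot be determined, because the imaging manual is not available.

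The consequence is limited to the supportive RANO-LGG response rate, for calls at or before confirmation, and to the progression date otherwise. One changed call is worth 5.9 points in Part 2 and 2.4 to 5.9 points in the pooled cohort, depending on the unstated Part 1 count. The number of subjects affected is unknown, and nothing in the documents shows that any call would change. The primary objectives, the investigator-assessed endpoint and the earlier independent RANO result are untouched. The conclusion rests on the assumptions in Step 3 and on reading RANO-LGG as confined to central review.

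**What to change.** In the new-lesion paragraph of the RANO-LGG section of Appendix 2, replace the investigator or local reader, in both places, with *the independent central reader, without access to the local lesion assessment*. Add one sentence stating that corticosteroid use and investigator-assessed clinical status are the only site inputs to the composite. Align the imaging manual, or, if it already assigns this call to the central reader, align Appendix 2 with it.

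The cost is two substitutions and one sentence in the protocol, plus a check of the manual. It needs no new scans, patient procedures or site work.

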4.2.2 Exclusion Criteria

Deviations from exclusion criteria are not allowed because they can potentially jeopardize the scientific integrity of the study, regulatory acceptability or subject safety. Therefore, adherence to the criteria as specified in the protocol is essential.

A subject will not be eligible for inclusion in this study if any of the following criteria apply:

1. **Part 2 ONLY:** Previous treatment with dabrafenib, another RAF inhibitor, or a MEK inhibitor (exception: prior treatment with sorafenib is permitted);
2. Malignancy OTHER than the BRAF mutant malignancy under study
3. Had chemotherapy or radiotherapy within 3 weeks (or 6 weeks for nitrosoureas or mitomycin C) prior to administration of the first dose of study treatment;
4. The subject has received an investigational product within the following time period prior to the first dosing day in the current study: 28 days or 5 half-lives or twice the duration of the biological effect of the investigational product (whichever is warranted by the data);
5. History of another malignancy;

Exception: (a) Subjects who have been successfully treated and are disease-free for 3 years, (b) a history of completely resected non-melanoma skin cancer, (c) successfully treated *in situ* carcinoma, or (d) CLL in stable remission, are eligible

6. Current use of a prohibited medication ([Section 8.2](#)) or herbal preparation or requires any of these medications during the study;
7. Unresolved toxicity greater than NCI CTCAE v4.0 ([NCI, 2009](#)) Grade 2 or higher from previous anti-cancer therapy, including major surgery, except those that in the opinion of the investigator are not clinically relevant given the known safety/toxicity profile of dabrafenib (e.g., alopecia and/or peripheral neuropathy related to platinum or vinca alkaloid based chemotherapy);
8. Has leukaemia;
9. History of allergic reactions attributed to compounds of similar chemical or biologic composition to dabrafenib and its excipients;
10. Autologous or allogeneic stem cell transplant within 3 months prior to enrolment [NOTE: subjects with evidence of active graft versus host disease are excluded];
11. History of myocardial infarction, severe or unstable angina, peripheral vascular disease or familial QTc prolongation;
12. Abnormal cardiac valve morphology (\geq grade 2) documented by echocardiogram (NOTE: subjects with grade 1 abnormalities [i.e., mild regurgitation/stenosis] can be entered on study);

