Any equivocal new lesions should continue to be followed. Treatment can continue at the discretion of the investigator until the next scheduled assessment. If at the next assessment the new lesion is considered to be unequivocal, progression should be documented.

Evaluation of Overall Response

Table 15-1 presents the overall response at an individual time point for all possible combinations of tumor responses in target and non-target lesions with or without the appearance of new lesions for subjects with measurable disease at baseline.

Table 15-1 Evaluation of Overall Response for Subjects with Measurable Disease at Baseline

Target Lesions	Non-Target Lesions	New Lesions	Overall Response
CR	CR or NA	No	CR
CR	Non-CR/Non-PD or NE	No	PR
PR	Non-PD or NA or NE	No	PR
Stable disease	Non-PD or NA or NE	No	SD

NE	Non-PD or NA or NE	No	NE
PD	Any	Yes or No	PD
Any	PD	Yes or No	PD
Any	Any	Yes	PD

CR=complete response, PR = partial response, PD=progressive disease, NA= not applicable, and NE=not evaluable

Note:

- Subjects with a global deterioration of health status requiring discontinuation of treatment without objective evidence of disease progression at that time should be classified as having "symptomatic deterioration." Objective response status is determined by evaluations of disease burden. Every effort should be made to document the objective progression even after discontinuation of treatment.
- In some circumstances, it may be difficult to distinguish residual disease from normal tissue. When the evaluation of CR depends on this determination, it is recommended that the residual lesion be investigated (fine needle aspirate/biopsy) to confirm the CR.

Evaluation of Best Overall Response

The best overall response is the best response recorded from the start of the treatment until disease progression/recurrence and will be determined programmatically by Novartis based on the investigators assessment of response at each time point.

- To be assigned a status of stable disease, follow-up disease assessment must have met the SD criteria at least once after first dose of study medication at a minimum interval of 12 weeks.

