- cystic or necrotic lesions (without a nodular component)
- other measurable lesions that cannot be considered as target lesions

Lesions composed of a tumor around a cyst or a surgical cavity are considered non-measurable unless there is a nodular component that measures 10 mm or more in 2 perpendicular diameters. The cystic or surgical cavity should not be measured for the determination of a response. Non-measurable lesions should all be followed as non-target lesions.

Target lesions should be assessed quantitatively at each of the time points specified in the protocol.

The updated response criteria for LGG are defined in the following tables. Please note that the minor response category is not used in this clinical trial. Patients meeting criteria for minor response will be considered to have stable disease for the purposes of this trial.

Response assessment of target lesions

Response Criteria	Evaluation of target lesions
Complete response (CR)	Complete disappearance of all measurable lesions on T2/FLAIR images sustained for at least 4 weeks.* No new or increased enhancement on T1 images.
Partial response (PR)	≥ 50% decrease, compared with baseline, in the sum of products of perpendicular diameters of all measurable lesions on T2/FLAIR sustained for at least 4 weeks.* No new or increased enhancement on T1 images.
Progressive disease (PD)	≥25% increase in sum of the products of perpendicular diameters of measurable lesions on T2/FLAIR images compared to nadir. Increased enhancement on T1 images showing evidence of malignant transformation.
Stable disease (SD)	Neither sufficient shrinkage to qualify for partial response nor sufficient increase to qualify for progressive disease. No new or increased enhancement on T1 images.
Not Evaluable (NE)	Not evaluable will be used in exceptional cases where one or more measurable lesions cannot be assessed or have been assessed using a different method than baseline, in absence of progressive disease documentation
* In the absence of a confirming scan 4 weeks later, this scan will be considered only stable disease.	

Response assessment of non-target lesions

Response Criteria	Evaluation of non-target lesions
Complete response (CR)	Complete disappearance of all non-measurable lesions on T2/FLAIR. No new or increased enhancement on T1 images.
NonCR/NonPD	Persistence of one or more non-measurable lesions on T2/FLAIR. No new or increased enhancement on T1 images.

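### The RANO-LGG criteria give two size rules for progression, one with steroid and radiation conditions and one without, and do not say which governs

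*Protocol*

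**What the plan says.** The RANO-LGG part of Appendix 2 (Section 15.2) was added for central independent review. It sets out progression in three places.

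- **Target-lesion table, PD row:** "≥25% increase in sum of the products of perpendicular diameters of measurable lesions on T2/FLAIR images compared to nadir". No steroid, radiation or comorbidity condition is attached to this size rule. The table's single footnote concerns confirmation scans.
- **Overall-response table, PD column:** "≥25% increase in SPPD compared to Nadir", with any one criterion sufficient. In the row "Corticosteroids compared to baseline" the PD cell reads NA. Several PD cells carry double or triple asterisks whose legends are not in the text available here.
- **PD list, item a:** "A 25% increase of the T2 or FLAIR non-enhancing lesion on stable or increasing doses of corticosteroids compared with nadir", with the further condition "not attributable to radiation effect or to comorbid events".

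A lead-in sentence says that the LGG criteria are defined in the tables. The lists then follow under the same heading as full definitions, and nothing ranks one form above the other. SAP Section 2.6.1 says only that the updated criteria will be used for independent review of LGG.

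The older RANO text in the same appendix attaches the steroid condition to PD by growth. For T2/FLAIR growth it also excludes comorbid events. It does not mention radiation effect.

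**The concern.** A central reader must make one call per scan. If the table makes growth PD and the list withholds PD because steroids are being reduced or radiation explains the change, the call depends on which paragraph the reader follows. Two readers could both comply with the protocol and still disagree on progression status and date.

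Both situations can arise here. The exclusion criteria (Section 4.2.2) bar a child who "Had chemotherapy or radiotherapy within 3 weeks" of the first dose (longer for some chemotherapy), so earlier radiotherapy is allowed. The pyrexia guidance (Section 3.7.4.1, Table 3-4) includes courses of oral corticosteroids and mentions tapering them. At stake is the reproducibility of the RANO-LGG independent reads that Amendment 11 introduced.

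**Working it through.** The plan gives no figure to reproduce. The check applies each rule to the same scan. The lesion areas are assumed for illustration, and no other PD criterion is taken to be met.

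**Input.** One measurable T2/FLAIR lesion, nadir 400 mm², now 520 mm². Change from nadir = 520/400 − 1 = +30%.

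| Circumstance | Target-lesion table | PD list, item a |
|---|---|---|
| Steroid dose stable or rising, no other cause | PD | PD |
| Steroid dose being reduced | PD | not PD |
| Growth judged radiation effect or comorbid event | PD | not PD |

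With one lesion, the sum of products and the product for that lesion are the same number. The disagreement in the last two rows therefore comes from the qualifiers alone, however the list's singular wording is read.

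**Is there another category for such a scan?** In the overall-response table, stable disease (SD) needs growth below 25% from nadir and all criteria met, so a +30% scan cannot be SD there. The SD list requires a stable non-enhancing area, so it does not clearly admit the scan either. The not-evaluable entries cover unassessed lesions and changed methods, and neither applies. A scan that the list exempts from PD thus has no stated home.

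**Weight of one child.** Amendment 11 reports 17 LGG subjects in Part 2, so 1/17 = 5.9 percentage points. For illustration, with exact 95% intervals:

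- 6/17 = 35.3% (14.2 to 61.7)
- 7/17 = 41.2% (18.4 to 67.1)

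SAP Section 2.1 also plans a pooled LGG cohort that adds Part 1 subjects, whose number is not given. Part 1 enrolled 27, of whom two had miscellaneous tumours, so at most 27 − 2 = 25 were LGG. The pooled denominator lies between 17 and 17 + 25 = 42, and one child is worth between 5.9 and 1/42 = 2.4 points.

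**The case against.** The best defence has three parts.

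First, the protocol points to the tables as the definition. That is a hint about precedence and not a rule, because complete lists with different conditions follow at once.

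Second, the target-lesion table is only a component. The overall response is a composite that includes steroid use and clinical status, and the missing footnotes there may carry the qualifiers. This stands in part. If the legends contain the steroid and radiation conditions, the overall-response table may agree with the list. The target-lesion row that feeds it would still be unqualified and would still need aligning.

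Third, the consequence is small. RANO-LGG is a supplemental read, the earlier RANO independent review is kept, the secondary endpoint is investigator-assessed, and no hypothesis is tested. This stands and limits the weight of the point.

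A reader might also infer three stronger things that the documents do not support:

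- **That size is measured per lesion in the lists and as a sum in the tables.** The lists do speak of one lesion, as in the partial-response (PR) item "Greater than or equal to 50% in the product of perpendicular diameters of the lesion on T2 or FLAIR imaging", which also omits the direction of change. Both tables use the sum, and the singular is probably loose wording for a single tumour. This is drafting to tidy, not a second demonstrated conflict.
- **That the tables lack qualifiers for response as well.** The overall-response table has steroid and clinical-status rows for complete response, PR and SD that broadly match the lists. The gap concerns the PD size rule.
- **That an early PD call shuts out a later response.** The sentence "The best overall response is the best response recorded from the start of the treatment until disease progression/recurrence" belongs to the RECIST part of the appendix and rests on the investigator's assessments. Carrying it over to the independent RANO-LGG reads is an inference. The SAP refers further efficacy details to an earlier sponsor SAP that is not among the documents.

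**Conclusion.** The contradiction is real. For growth of at least 25% from nadir, the target-lesion table and PD list item a give opposite calls when steroids are being reduced or when the growth is attributed to radiation effect or comorbid events. No precedence is stated.

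This conclusion assumes only that such growth is the sole candidate PD criterion on the scan. The overall-response footnotes should be checked in the full document before the wording is settled. The effect is limited to the supplemental independent LGG review. The step of 5.9 points (2.4 at the lowest if pooled) is the weight of one reclassified child, not an estimate of bias, and the documents do not show how many reads would change. The point merits correction because the remedy is cheap and the classification of independent reads depends on it. It does not threaten the trial's main conclusions.

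**What to change.** State one PD size rule and say which text governs. A workable rule is a rise of at least 25% from nadir in the SPPD of the measurable T2/FLAIR lesions, counted only while the corticosteroid dose is stable or rising, and only when neither radiation effect nor a comorbid event explains it. Use it identically in the target-lesion table, the overall-response table (including its steroid cell and footnotes) and the PD list.

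Qualifying the PD cells alone is not enough, because the SD cell would still exclude the same scan. Amend that cell and the SD list so that growth of 25% or more that fails the qualifiers has a stated category, either SD or not evaluable.

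As clean-up in the lists, replace the singular lesion with SPPD, insert the missing word for a decrease in PR item a, and delete the leftover MR from the SD list, since minor response is not used in this trial.

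Apply the single rule to every RANO-LGG independent read. Steroid doses and dates (Section 8.1) and prior radiotherapy (Table 3-7) are already recorded. Attribution to radiation remains the reader's judgement. The cost is wording in Appendix 2 and in any independent-review charter, and possibly re-adjudication of a few reads.
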